12.1.1 Adverse Events of Special Interest

Adverse events of special interest will include psychiatric events of interest (categorized as psychosis/mania, suicidal, aggression and other events) listed in Table 2. Adverse event terms of special interest will be searched across the TEAE data and summarized with the total exposure (in subject-days).

 Table 2
 Psychiatric Events

Category	Preferred Term/Verbatim term
Signs and/or symptoms of psychosis/mania	Hallucination (any type, including visual, auditory, tactile, mixed, etc.)
	Delusion (any type including somatic, persecutory, grandeur, reference)
	Schizophrenia (any type)
	Psychotic disorder
	Transient psychosis
	Acute psychosis
	Paranoia
	Childhood psychosis
	Schizophreniform disorder
	Schizoaffective disorder
	Catatonia
	Mania
	Hypomania
Suicidal ideation and behavior	Depression suicidal
	Gun shot wound
	Intentional self-injury
	Non-accidental overdose
	Overdose
	Self injurious behavior
	Self injurious ideation
	Self-mutilation
	Suicidal ideation
	Suicidal attempt
	Completed suicide
Aggression and violent behavior	Aggression
	Anger
	Hostility
	Homicidal ideation
	Sexual offense
	Murder
	Imprisonment

Table 2 Psychiatric Events

Category	Preferred Term/Verbatim term			
Miscellaneous psychiatric events (include	Abnormal behavior			
events with serious outcome only)	Agitation			
	Amnesia			
	Confusional state			
	Depressed mood			
	Depression			
	Disorientation			
	Emotional disorder			
	Emotional distress			
	Feeling abnormal			
	Memory impairment			
	Mood altered			
	Mood swings			
	Personality change			
	Thinking abnormal			
	Anxiety			
	Fearfulness			
	Phobia			
	Panic attack			
	Sleep disturbance			
	Ties			
	Obsessive or compulsive behavior			
	Trichotillomania			

A separate listing will be provided for AEs of special interest.

Adverse events of particular interest include insomnia (including AEs with preferred terms of 'INSOMNIA', 'INITIAL INSOMNIA', 'MIDDLE INSOMNIA', and 'TERMINAL INCOMNIA'), weight decrease and decreased appetite. The preferred terms for these 3 AEs will be reviewed prior to database lock to determine which will be used to identify them.

For each of these 3 AEs, the following information will be presented by treatment group:

- Number and percentage of subjects reporting the TEAE
- Number of TEAEs
- Summary of onset day of first TEAE: The onset day of first TEAE is calculated as (onset date of first TEAE-date of first dose) + 1 for subjects who experienced the TEAE
- Summary of duration of TEAE while on study drug: The duration of each event is the number of days from the onset of the TEAE, while on study drug during SHP465 6.25 mg, until the earlier of the end date of the TEAE or the date of last dosing + 3 days (if the date of last dosing is missing, the date of last day on study will be used). TEAEs that either overlap in time, or are adjacent in time will be merged into one TEAE only for the purposes of calculating duration of event. If a subject has multiple TEAEs that

Protocol SHP465-309

are not overlapping or adjacent in time, the durations will be averaged for that subject. Summary statistics are then based on the averaged subject durations. The calculated duration only includes the duration of TEAEs.

- Number and percentage of mild, moderate and severe TEAEs: Overlapping TEAEs with different preferred terms are counted as multiple TEAEs.
- Summary of the number of TEAEs per subject: Overlapping TEAEs with different preferred terms are counted as multiple TEAEs.
- Number and percentage of TEAEs that:
 - Resolved while on study drug
 - Ongoing
 - Dose interrupted
 - Dose withdrawn (and other action categories related to dose)
 - TEAEs leading to discontinuation
 - Number of subjects who discontinued investigational product due to the event

Also, for each of these 3 AEs, the following information will be presented by week:

- Number of subjects in the study
- Number and percentage of subjects with the TEAE
- Number of TEAEs
- Number and percentage of subjects who discontinued due to the TEAE
- Number and percentage of mild, moderate and severe TEAEs. If a subject has more than one TEAE in the same week, then the worst severity is counted.

Where, Week 1 includes TEAEs that start after Visit 2 (Baseline) through Visit 3 (Week 1), Week 2 includes TEAEs that start after Visit 3 (Week 1) through to Visit 4 (Week 2), Week 3 includes TEAEs that start after Visit 4 (Week 2) through to Visit 5 (Week 3), and Week 4 includes TEAEs that start after Visit 5 (Week 3) through to Visit 6 (Week 4).

In addition, for each subject, all occurrences of each of these 3 AEs will be listed separately by treatment group, subject, start date and stop date. The information presented will include: subject, sex, age, race, ethnicity, preferred term/adverse event, start date, stop date, onset day, study visit, last dose date, duration/imputed duration of TEAE (days), SAE, severity, effect on dosing and treatment for AE.

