16. DATA MONITORING/REVIEW COMMITTEE

An external independent Data Monitoring Committee (DMC) was set up to review the data pertaining to safety and tolerability of the study therapy for the duration of this program, which includes studies SHP465-112, SHP465-308, and SHP465-309. The DMC will review the data pertaining to safety and tolerability of the study therapy. Active surveillance for insomnia and decreased appetite leading to weight loss are included. Confidentiality of the unblinded DMC analyses is a critical concern and to address this, an unblinded independent reporting team will be identified within a CRO. The independent reporting team will have no involvement in the conduct of the study. Further details regarding the DMC can be found in the DMC charter, which will be available before the administration of investigational product.

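### The by-week summaries of insomnia, weight decrease and decreased appetite in SAP 12.1.1 count onsets but are worded as subjects with the event, so they cannot show whether events persist or resolve

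*SAP*

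**What the plan says.** SAP 12.1.1 singles out three adverse events, insomnia plus "weight decrease and decreased appetite. The preferred terms for these 3 AEs will be reviewed prior to database lock", and gives them two kinds of summary.

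The first is by treatment group over the whole treatment period. It covers onset day, duration on drug, severity, and counts of events resolved or ongoing. A listing gives start and stop dates for every occurrence.

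The second is weekly: "Also, for each of these 3 AEs, the following information will be presented by week". Its rows include "Number of subjects in the study" and "Number and percentage of subjects with the TEAE", followed by the number of events, discontinuations and severity. The weeks are then defined by start date. The rule for the first is "Week 1 includes TEAEs that start after Visit 2 (Baseline) through Visit 3 (Week 1". The second and third weeks follow the same pattern, and the rule for the last is "Week 4 includes TEAEs that start after Visit 5 (Week 3) through to Visit 6 (Week 4". No rule carries an ongoing event into a later week.

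Three other rules bear on this:

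- Protocol 8.1.1 has sites open a new event whenever severity changes.
- SAP 12.1.1 merges overlapping or adjacent records, but for the duration calculation only.
- Protocol 9.10 and SAP 12.1 let an event count as treatment-emergent up to 3 days after the last dose.

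**The concern.** A row described as subjects with the event, set beside the number of subjects in the study that week, reads as the share of children affected in that week. The counting rule delivers something else: children for whom a record opened in that week. If onsets cluster early, the row falls over the four weeks whether the events resolve or continue unchanged, and a reader could take the fall as growing tolerance.

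Persistence matters for these events. Protocol 7.2.4.12 requires discussion with the medical monitor when sleep difficulties are clinically significant and persistent, or when weight loss reaches 7%. SAP 16 says of the data monitoring committee's review: "Active surveillance for insomnia and decreased appetite leading to weight loss are included". That shows the priority given to these events. It does not show that the committee uses this table.

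**Working it through.** The documents give no figure for this point, so there is none to reproduce. The check applies the SAP's rule to assumed event histories and compares it with a count of children who have the event at any time in the week.

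**Inputs.** Arm size is 60 / 2 = 30 (protocol 9.7, 1:1 randomization). The week rule is that of SAP 12.1.1. Assumed for illustration: 6 children with onset in Week 1, 1 with onset in Week 2, no dropout, no severity change.

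**Step 1: three histories under both rules (children in Weeks 1, 2, 3, 4).**

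| History | SAP rule (start in week) | Event present in week |
|---|---|---|
| All 7 persist to Week 4 | 6, 1, 0, 0 | 6, 7, 7, 7 |
| 3 of the 6 Week 1 events persist; the other 4 events last one week | 6, 1, 0, 0 | 6, 4, 3, 3 |
| All 7 last one week | 6, 1, 0, 0 | 6, 1, 0, 0 |

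The SAP row is 20.0%, 3.3%, 0%, 0% of 30 in every case. In Week 4 the share actually affected is 7/30 = 23.3%, 3/30 = 10.0% or 0/30 = 0%. One tabulated row fits all three histories.

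**Step 2: affected child-weeks not shown.**

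- All persist: 6 + 7 + 7 + 7 = 27 affected, 7 shown, 20/27 = 74% not shown.
- Half of the Week 1 events persist: 6 + 4 + 3 + 3 = 16 affected, 7 shown, 9/16 = 56% not shown.
- All last one week: 7 affected, 7 shown, 0% not shown.

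**Step 3: the bounds.** One unbroken event of constant severity, present from week s to week e, covers e − s + 1 weeks and is shown once. The share not shown is (e − s)/(e − s + 1). This is 0 when e = s, and at most 3/4 = 75%, when s = 1 and e = 4. For example, 6 children affected in all four weeks give 24 child-weeks, of which 6 are shown and 18/24 = 75% are not.

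**Step 4: severity changes.** Take two children with severe insomnia from Week 1 to Week 4. In the first it stays severe: the table shows this child in Week 1 only. In the second it becomes mild in Week 3: protocol 8.1.1 opens a new record, and the table shows this child in Week 1 and again in Week 3. The improving child is counted twice and the unimproved child once. Merging adjacent records would put both in Week 1 only, but the SAP restricts merging to duration.

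**Step 5: denominator.** The only count listed beside the row is all subjects in the study, which includes children who already have the event. In the first history, Week 2 has 30 − 6 = 24 children free of the event at its start. The onset proportion is then 1/24 = 4.2%, against 1/30 = 3.3%.

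**Step 6: end of the window.** Week 4 closes at Visit 6, while treatment-emergent events run to last dose + 3 days. An event that starts after Visit 6 but inside that window is in the overall tables and in no week, so the weekly counts need not add up to the overall count.

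**The case against.** The strongest reply is that persistence is already reported. SAP 12.1.1 gives duration on drug, resolved and ongoing counts, and a dated listing for the same three events. SAP 12.5.2 and 12.5.3 summarize both sleep questionnaires by visit. SAP 12.3 does the same for weight change and for weight loss of at least 7%. A false impression of tolerance in sleep or weight could be checked against these. This stands, and it confines the point to the by-week display. It does not remove the point, because none of these outputs gives the weekly share of children affected by the adverse event. For decreased appetite the SAP describes no other by-visit summary.

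A second reply is that a weekly onset table is a legitimate display and that the SAP states its start-date rule openly. Table specifications are in a separate document (SAP 1 and 21), so final titles and footnotes are unknown, and the SAP does not expressly say that the subjects-in-study row is the percentage denominator. This also stands. It makes relabelling part of the remedy, but a label alone would not deal with split records, the late events or the missing weekly prevalence.

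A reader might infer more: that the rows must fall to zero by construction, or that persistent events disappear from the safety reporting. The documents support neither. The rows fall only if onsets are early, since later first onsets, second episodes and severity-change records all count in later weeks. Persistent events remain visible in the overall summary and the listing.

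**Conclusion.** The point holds for the by-week summaries only. As specified they are onset counts, worded as subjects with the event, and they cannot distinguish events that persist from events that resolve. They can count an improving event as a further one, and they leave out events that start after Visit 6 within the 3-day window.

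The share of affected child-weeks not shown lies between 0% and 75%, taking unbroken events of constant severity and no dropout. Where it would fall depends on when events start and how long they last, which the documents do not fix. The 75% is the worst case and not an expected value. The output is descriptive, and no efficacy result or overall adverse-event count is affected. A cheap improvement is worth making; the analysis is not invalid without it.

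**What to change.** In SAP 12.1.1, for each of the three events:

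1. Relabel the present rows as *subjects with new onset in the week*. First merge overlapping or adjacent records, as is already done for duration. Use children free of the event at the start of the week as the denominator.
2. Add a row for children with the event present at any time in the week: started on or before the end of the week and not stopped before it began. The denominator is children in the study that week. Show the worst severity present.
3. State a stop-date convention, because SAP 19.7 leaves incomplete adverse-event stop dates unimputed. Treat a missing or incomplete stop date as ongoing unless the known part shows that the event ended earlier.
4. Extend the last interval to last dose + 3 days, so that every treatment-emergent event falls in a week.

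The cost is one extra block per table and one stop-date convention. Start and stop dates are already collected and listed, and nothing now planned is removed.

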12.2 Clinical Laboratory Variables

Descriptive statistics for clinical laboratory values (in SI units) and changes from Baseline to Visit 6/ET as well as shift tables from Baseline to Visit 6/ET for quantitative variables will be presented by treatment group for the following clinical laboratory variables:

Shire CONFIDENTIAL Page 35

Statistical Analysis Plan Protocol SHP465-309

Version 2.0/16 Aug 2018

Biochemistry and Endocrinology

Total cholesterol Calcium Aspartate aminotransferase Uric acid

Phosphorus

Alanine aminotransferase

Total bilirubin

Sodium

Creatinine

Alkaline phosphatase

Potassium

Gamma-glutamyl transferase

Blood urea nitrogen

Total bilirubin

Greatinine

Albumin

Total protein

Thyroid-stimulating hormone Lactate dehydrogenase

Free thyroxine

Hematology

Hemoglobin

Hematocrit

Red blood cells

Platelet count

White blood cell count – total and differential

Mean corpuscular hemoglobin

Neutrophils

Lymphocytes

Monocytes

Eosinophils

Basophils

Bands

Mean corpuscular hemoglobin concentration Mean corpuscular volume

Urinalysis

Glucose pH

Specific gravity Urobilinogen

Blood Color

Ketones Leukocyte esterase

Protein Nitrate

Bilirubin

Microscopic examination will be conducted if protein and/or blood is/are detected during urinalysis. At a minimum the microscopic examination will consist of red blood cells, white blood cells, casts, and bacteria.

Clinical laboratory test values are potentially clinically important (PCI) if they meet either the low or high PCI criteria listed in Table 3. The number and percentage of subjects with post-baseline PCI values will be tabulated. The percentages will be calculated relative to the number of subjects with available baseline values and at least 1 post-baseline assessment. The numerator is the total number of subjects with at least 1 post-baseline PCI value. A supportive listing of subjects with post-baseline PCI values will be provided including the subject number, baseline, and post-baseline values.

 Table 3
 Criteria for Potentially Clinically Important Laboratory Tests

Parameter	PCI Criteria						
Biochemistry							
Cholesterol-H	>300mg/dl** (>7.8mmol/L)						
Glucose, serum	<55mg/dl or >160mg/dl (<3.1mmol/L or >8.9mmol/L)						
Bilirubin, total	>1.5 x ULN						
Transaminase, SGOT, AST	>3 x ULN						
Transaminase, SGPT, ALT	>3 x ULN						
Gamma Glutamyl Transpeptidase (GGT)	>3 x ULN						
Alkaline phosphatase	>2.5 x ULN						
Lactate dehydrogenase (LDH)	>3 x ULN*						
Sodium	<130mEq/L (grade 3) or >150mEq/L (mmol/L)						
Potassium, serum/plasma	<3mEq/L (grade 3) or >5.5mEq/L (mmol/L)						
Calcium	<8mg/dl or >11.5mg/dl (<2mmol/L or >2.9mmol/L)						
Phosphorus, inorganic	<2.5mg/dl or >7.0mg/dl** (<0.8mmol/L or						
	>2.3mmol/L)						
Uric acid, serum	>10mg/dl (>0.6mmol/L or >594.8μmol/L)						
Thyroid Stimulating Hormone (TSH) ~	$< 0.35 \mu IU/ml \text{ or } > 6 \mu IU/mL (0.35 m IU/L \text{ or } > 6 m IU/L)$						
Blood Urea nitrogen (BUN)	>2.5 x ULN* (or alternatively >30mg/dl**,						
	>10.7mmol/L)						
Creatinine, serum	>1.5 x ULN (or alternatively >2mg/dl**, >176.8μmol/L)						
Albumin	<3g/dl (<30g/L)						
Total protein, plasma or serum	<5g/dl* or >9g/dl* (<50g/L or >90g/L)						
Hematology							
Hemoglobin (He.)	<10g/dl (<100g/L)						
Hematocrit	<32% or >45% (<0.32 or >0.45 Fraction of 1)						
Red Blood Cells (RBC)	male: <2.5 x106/μL; female: <2.0 x106/μL						
	(male: <2.5 x 10 ¹ 2/L; female: <2.0 x 10 ¹ 2/L)						
Mean Corpuscular Hemoglobin (MCH)	< LLN or $>$ 32pg						
Mean Corpuscular Volume (MCV)	< 70 fL or > 110 fL						
Mean Corpuscular He. Concentration (MCHC)	< 28g/dL or > 41g/dL (< 280g/L or > 410g/L)						
Platelet count	<75 x 109/L or >500 x 109/L						
White Blood Cell Count (WBC)	$<3 \times 109/L \text{ or } > 16 \times 109/L$						
Bands	> 5%						
Neutrophils	< 15%						
Eosinophils	> 10%						
Basophils	> 15%						
Lymphocytes	> 80%						
Monocytes	> 40%						
ANC (%neutrophils x WBC count)	<1.3x10e9/L						
Urinalysis							
Glucose	Positive Value (excluding trace)						
Blood	Positive Value (excluding trace)						
Ketones	Positive Value (excluding trace)						
Protein	Positive Value (excluding trace)						
Bilirubin	Positive Value (excluding trace)						

Version 2.0/16 Aug 2018

Table 3 Criteria for Potentially Clinically Important Laboratory Tests

Parameter	PCI Criteria		
Leukocyte Esterase	Positive Value (excluding trace)		
Nitrite	Positive Value (excluding trace)		

^{*}The NCI has not specified a value, Shire physicians have agreed on lab values provided.

ULN: Upper limit of normal value provided by the laboratory; LLN: Lower limit of normal value provided by the laboratory

All laboratory data will be listed for the Safety Set.

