12.4 Electrocardiogram (ECG)

Electrocardiogram results and change from baseline will be summarized at each visit and at the FoTA by treatment group. If there are multiple assessments for the interpretation at any visit, the worst interpretation will be used in the summary tables. For the interval parameters at post-baseline visits, the first readable result will be used if there are multiple assessments.

For the ECG interval parameters, baseline is defined as the average of all valid ECG measurements as the last assessment obtained prior to the first dose of the investigational product. For the ECG interpretation, baseline will be the ECG with the worst interpretation obtained at the baseline Visit (Visit 2), providing this is prior to the first dose of the investigational product.

PCI criteria will be applied to all ECG data at each visit including any repeat/unscheduled assessments and presented by visit and treatment group. PCI criteria are defined in Table 7.

Table 7 Cr	riteria for Potent	ially Clinically	/ Important ECG Valu	ues
------------	--------------------	------------------	----------------------	-----

ECG Parameter	Outlier Criteria
ECG result	Shift from a normal baseline to an abnormal finding or from
	an abnormal baseline to a new abnormal finding
Heart rate	≤50 beats/minute* or ≥100 beats/minute*
PR interval (increase)	≥200 msec*
QRS interval	≥120 msec*
QTcF/QTcB	≥450 msec* and <480 msec*
	≥480 msec* and <500 msec*
	≥ 500msec*
QT/QTc from Baseline	≥30 msec* and <60 msec*
	≥60 msec*

^{*}The NCI has not specified a value, Shire physicians have agreed on values provided. ECG=electrocardiogram; QTcB=Bazett's corrected QT interval; QTcF=Fridericia's corrected QT interval

is the total number of subjects with at least 1 PCI post-baseline ECG value.

The number and percentage of subjects with post-baseline PCI values will be tabulated. The percentages for the observed value criteria will be calculated relative to the number of subjects with at least 1 post-baseline assessment available per parameter and visit. The percentages for the change from baseline criteria will be calculated relative to the number of subjects with available baseline and at least 1 post-baseline assessment per parameter and visit. The numerator

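### The laboratory PCI table and the ECG observed-value PCI rows count pre-existing abnormalities together with new ones, and the SAP does not say that low and high values are tabulated separately

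*SAP*

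**What the plan says.** **Laboratory (SAP 12.2, Table 3).** Values are PCI "if they meet either the low or high PCI criteria listed in Table 3". Percentages are taken "relative to the number of subjects with available baseline values and at least 1 post-baseline assessment", and the count rule is: "The numerator is the total number of subjects with at least 1 post-baseline PCI value". The baseline value is needed to enter the denominator but plays no part in the numerator. Low and high limits share one entry in the criteria table; potassium, for example, reads "<3mEq/L (grade 3) or >5.5mEq/L (mmol/L".

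**ECG (SAP 12.4, Table 7).** For the observed-value criteria the denominator needs only a post-baseline assessment, and the numerator "is the total number of subjects with at least 1 PCI post-baseline ECG value". Heart rate carries both directions in one entry: "≤50 beats/minute* or ≥100 beats/minute".

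**Assessments used.** SAP 19.4 brings all post-baseline assessments into the PCI determination, repeats and unscheduled ones included, with no baseline condition.

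**Neighbouring outputs.** SAP 12.2 states that "shift tables from Baseline to Visit 6/ET for quantitative variables will be presented by treatment group". It also plans a PCI listing that "will be provided including the subject number, baseline, and post-baseline values". SAP 12.4 plans a baseline-to-FoTA shift table of the ECG evaluation. SAP 12.3, Table 4 has separate low and high pulse criteria, each also in a version that requires a change from baseline of more than 15 beats/minute.

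**The concern.** A PCI table by arm is read as a list of abnormalities that appeared on treatment. Here a child whose MCH was below the lower limit, whose eosinophils were above 10%, or whose urine dipstick was positive before the first dose counts the same as a new case if the finding is still present afterwards.

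Eligibility does not prevent this. Protocol exclusion criterion 12 (section 4.2) bars abnormalities that are clinically significant. That is not tied to the limits in Table 3 or Table 7.

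Elsewhere the SAP does condition on baseline. A TEAE must start or worsen after the first dose (SAP 12.1), and two of the six Table 7 criteria are baseline-relative. The laboratory table and the ECG observed-value rows are the exception.

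Direction is a second, smaller matter. If a low and a high value fall into one count, the reader cannot tell from the table whether a parameter moved down or up. For a drug that the protocol (section 1.2.1) associates with a mean heart-rate rise of about 3–6 bpm, direction matters for heart rate in particular.

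**Working it through.** There is no figure in the plan to reproduce. The check is a count of the criteria affected, then an illustration of scale.

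**1. Criteria affected.**

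| Table | Parameters | Not conditioned on baseline | Both a low and a high limit |
|---|---|---|---|
| SAP Table 3 (laboratory) | 40 = 18 biochemistry + 15 hematology + 7 urinalysis | 40 | 13 |
| SAP Table 7 (ECG) | 6 | 4 (heart rate, PR, QRS, QTcF/QTcB) | 1 (heart rate) |

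The 13 two-sided laboratory parameters are glucose, sodium, potassium, calcium, phosphorus, TSH, total protein, hematocrit, MCH, MCV, MCHC, platelets and WBC. Of the other 27, 20 have one limit and 7 are urinalysis positives. PR is treated as an observed-value row because its limit is an absolute 200 msec.

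**2. Size, by assumption.** Let n = 30 per arm (about 60 randomised 1:1), p = proportion already PCI at baseline, s = probability that such a child is PCI again after baseline, and i = new-onset probability in the rest.

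- SAP count = n × [p·s + (1 − p)·i]
- New cases = n × (1 − p)·i
- Pre-existing share = p·s / [p·s + (1 − p)·i]

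Assumed ranges: p 2–20%, s 50–80%, i 3–10%.

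| p | s | i | SAP count (rate) | New cases | Pre-existing share |
|---|---|---|---|---|---|
| 2% | 50% | 10% | 3.24 (10.8%) | 2.94 | 9% |
| 2% | 50% | 3% | 1.18 (3.9%) | 0.88 | 25% |
| 10% | 50% | 3% | 2.31 (7.7%) | 0.81 | 65% |
| 10% | 80% | 3% | 3.21 (10.7%) | 0.81 | 75% |
| 10% | 80% | 10% | 5.10 (17.0%) | 2.70 | 47% |
| 20% | 80% | 10% | 7.20 (24.0%) | 2.40 | 67% |
| 20% | 80% | 3% | 5.52 (18.4%) | 0.72 | 87% |

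Worked line (p = 10%, s = 50%, i = 3%): 30 × (0.050 + 0.027) = 2.31; 30 × 0.027 = 0.81; 0.050/0.077 = 65%.

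**3. Between-arm comparison.** Randomisation makes p equal across arms in expectation. If s is also equal, p·s cancels and the expected difference is (1 − p) times the difference in new onset. With p = 10% and s = 80%, new-onset rates of 3% and 10% would appear as 10.7% and 17.0%. The difference is 6.3 points instead of 7.0, and the ratio is 17.0/10.7 = 1.6 instead of 10/3 = 3.3. The contrast is diluted and noisier, but not tilted towards either arm.

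**The case against.** **Much of the information appears elsewhere.** Laboratory tests have one scheduled post-baseline visit (Visit 6/ET). SAP 12.2 gives change from baseline, shift tables for quantitative variables and a listing with baseline beside post-baseline values. With about 60 children, that listing shows status and direction case by case. This stands in part. The shift categories are not defined or tied to the PCI limits, the 7 urinalysis positives have no stated shift table, and the ECG shift table covers the overall evaluation, not heart rate or intervals. A reader would still have to rebuild the between-arm comparison by hand.

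**Tachycardia is already covered.** Table 4 includes pulse of at least 100 with a rise of more than 15 from baseline, also on consecutive visits. SAP 12.3 adds pulse bands and age- and sex-specific 99th-percentile counts. Pulse is a triplicate average at four post-baseline visits, against two scheduled ECG visits. This largely stands: new tachycardia would not go unseen.

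**Pooling is not stated.** A reader might infer that the tables definitely merge low with high. The SAP defines when a value is PCI, and SAP section 1 puts table specifications in a separate document. All that can be said is that the SAP does not require separate rows.

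**Not every ECG row is affected.** A reader might extend the point to all ECG PCI counts. The ECG result criterion requires a shift to a new abnormal finding, and the QT/QTc change criterion has its own baseline-dependent denominator. PR, QRS and QTc run in one direction only.

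**The size is easily overread.** Normal curves fitted to the 1st and 99th percentiles in SAP Table 5 put pulse ≥100 at 12.7% of boys aged 6–8 (mean 86.5, SD 55/4.652 = 11.8) and 18.0% of girls (mean 89, SD 56/4.652 = 12.0), with about 5–11% in the older groups. From this a reader might infer about 3 children per arm with ECG heart-rate PCI before dosing. If 10% are pre-existing cases, two Binomial(30, 0.10) counts differ by 3 or more 27% of the time (13% at a prevalence of 5%, 36% at 15%). But Table 5 is resting pulse, not ECG rate; the curve shape is assumed; and the documents give no baseline PCI rate. Nor would the fix remove all of that noise. With 11% prevalence and an assumed between-visit correlation of 0.3–0.7, the per-visit chance falls from about 30% to about 24–16%.

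**Conclusion.** The point holds as a weakness in how safety data are displayed. All 40 laboratory criteria and 4 of the 6 ECG criteria count pre-existing and new PCI values alike. Separate low and high rows are not specified for 13 laboratory parameters and ECG heart rate.

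Its size cannot be fixed from the documents. The 9–87% range rests wholly on the assumed baseline, persistence and onset rates. The claim of noise and not bias rests on randomisation and on equal persistence in both arms.

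The plan calls these values post-baseline and never treatment-emergent, so nothing is mislabelled or contradicted. The primary analysis, power and type I error are unaffected. This is a minor, optional improvement, worth making because it is cheap and the other outputs only partly replace it.

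**What to change.** Keep the any-post-baseline count, so that persistence or worsening of an already-PCI value stays in the table. Add to SAP 12.2, and to SAP 12.4 for the observed-value criteria:

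- (a) separate low and high rows for the 13 two-sided laboratory parameters and for ECG heart rate;
- (b) a treatment-emergent row whose numerator and denominator are both limited to children with a baseline value that did not meet the criterion in the same direction. A shift table on the PCI limits that includes the urinalysis positives would serve equally well.

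The cost is SAP wording and table programming on data already collected. The tables gain a few rows, and the added rows have slightly smaller denominators: 27 of 30 per arm if 10% are PCI at baseline (30 × 0.90).
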